Accepting an alpha risk of 0.05 and a beta risk of 0.2 in a bilateral contrast, 165 individuals in the intervention group and 165 in the control group are required to detect a minimum relative risk of 7.8 (= 7.8% / 1%) taking the rate of VAD in the intervention group as 7.8% and in the control group of 1%. A rate of loss has been estimated for refusing the 10% share. The POISSON approximation has been used in the statistical calculator GRANMO, version 7.12 online (Program of Research in Inflammatory and Cardiovascular Disorders, Institut Municipal de Investigació Mèdica, Barcelona, Spain)

Although hypothetically no losses are expected, they may have been relinquished to participate for different reasons. In order to avoid a selection bias produced by the relationship of giving up with the fact of wanting to do a VAD, patients refusing to participate will be excluded and the motive, age and sex will be collected to compare if there are differences between the two groups regarding these characteristics.

Ambit

Florida Nord de l'Hospitalet de Llobregat Primary Care Center, an urban area with a population of approximately 25,000 people. Multicultural neighborhood with low socioeconomic status. The follow-up time for the intervention will be 3 months.

Information sources

Records of shared clinical history in eCAP. Patient questions about independent variables if they are not recorded.

Recruitment procedure

Consecutive recruitment: They will be consecutively obtained from different quotas (both afternoon shift and morning shift) so that the sample is representative of the study population.

Participate the quotas of the center whose doctor in charge has wanted to participate in the study. In order to avoid a selection bias and a more active doctor than another to have more patients represented in the study, a mechanism will be established whereby everyone will have the same probability of recruiting a similar number: the first 6 visits of each day for 8 days. The recruitment period will be made from 01/06/2015 to 09/30/2015, until the sample is completed. The follow-up period will be 3 months for each patient (both intervention and control).

A list of random numbers will be created and divided among the 7 consultations of the participating physicians in the study. Each day, the first 6 visits to the list will be recruited for 8 days prior appointment or until the sample is completed.

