Patients will be randomized according to the list of random numbers guarded by a professional (or several) other than the study that will be located in the adjacent consultation. In case there is no professional close, the list will be delivered with a

closed envelope to another professional and will be contacted by telephone. Patients will be treated with the intervention when the number is 1 and control if it is 0. This number will be asked prior to the patient's entry into the consultation.

Predictive or independent variables to be obtained at the time of the first visit

For stratified analysis.

- Sex: Male, Female
- Race: Caucasian vs non-Caucasian
- Age in years
- Level studies: Primary, secondary, university, without studies.
- Comorbidity: measured by the Charlson index. Score: a) 0-1: no comorbidity; b) 2: low comorbidity; c) ≥ 3 : high comorbidity.
(Charlson.webloc calculator).
- Testament on material goods: Yes, no.
- Religious Confession: yes, no. Is considered a practitioner: yes, no
- Marital status: single, married, widowed, separated / divorced
- Number of children

To obtain this information will be extracted from the computerized medical history or the patient will be asked.

Intervention

Patients who are included in the intervention group, if they meet the inclusion criteria and do not present any exclusion criteria, will be given brief information about the existence of the document of anticipated wills after resolving the reason for the visit for which they had come the patient. This information will not last more than 3 minutes and will not be repeated on successive visits within the recruitment period. Also, an informative triptych (see attachments) will be given to the patient so that he can read it at home. These leaflets have been made by the Department of Health of the Generalitat de Catalunya. They will be advised that we can extend the information if they are interested or help them to do the document in the near future if they want, we will inform you that we would wait for the answer before 3 months (24). In case of interest, you can leave your information in the User Service of the outpatient clinic by specifying name, telephone number and reference doctor or ask for an appointment again.

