Patients who fall into a control group will only be attended to their reason for visiting and will be asked for the necessary data to obtain the independent variables if they do not appear in their history. If the patient in this group wants the information, he will be excluded from the study because he "refuses to participate."

If the patient, both the control group and the intervention group, has some exclusion criteria, it will be recorded as a screening failure and their randomization number will not be re-used for the next patient.

All patient information will be kept confidential.

Result or dependent variables

They will be obtained at the moment that the patient shows interest in the intervention, or else, by asking by appointment or by telephone within 3 months of their recruitment:

- Interest in information about DVA: yes, no. Number of patients who have come to their family doctor (MF) to request information or have been interested by telephone in each group.

- Implementation of DVA: yes, no. Number of patients in each group.

In case of not being able to contact the telephone patient or face to face at 3 months, the DVA registration will be viewed at the Primary Care Clinic Station (eCAP), which is the computerized medical history program used by all professionals in the network of primary care of the Institut Català de la Salut (ICS).

The document can be accessed from:

- HC3 - Notices: shared clinical history projects in Catalonia.

- Dades del pacient: Documents of anticipated voluntats

Registration from the Department of Health is autonomous, although not done in the ABS. From other institutions, the patient is always advised to take the DVA to his health center.

- Open question to know the reason that has led to formalize the DVA, both to patients in the intervention group and control.

- Time to perform the DVA from the day of recruitment, expressed in days, to both the intervention and control patients.

Limitations and ethical considerations

- Possible increase in response in the intervention group due to the link with the family physician (participation bias). It could be wrongly concluded that the intervention is effective when compared to the control group. Randomization of the sample is intended to partially avoid this problem.

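### The allocation number is drawn before eligibility and consent are settled, failures use up numbers, and the protocol does not say whether 8 days or a completed sample ends recruitment

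*Protocol*

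**What the plan says.** **Order of events.** Under Recruitment procedure, the random list is held by someone outside the study, with 1 for intervention and 0 for control. On timing: "This number will be asked prior to the patient's entry into the consultation". The Intervention section then applies the eligibility criteria to patients already placed in a group. For a patient in either group with an exclusion criterion, "it will be recorded as a screening failure and their randomization number will not be re-used for the next patient". The exclusion list under Sample includes unwillingness to participate, so the same rule reaches refusals. A control patient who asks for the information is also removed and classed as a refusal.

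**Number of visits.** Each of the 7 participating doctors recruits from "the first 6 visits of each day for 8 days", a device meant to keep recruitment similar between doctors. One sentence gives the 8 days and completion of the sample as alternatives joined by *or*. Another ties completion of the sample to a calendar window of months in 2015. The Schedule of activities gives one month, September 2016.

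**Sample size.** "165 individuals in the intervention group and 165 in the control group are required", with the allowance worded as "A rate of loss has been estimated for refusing the 10% share". No allowance for ineligible patients is stated.

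**Analysis.** The Protocol's analysis section and the SAP both commit to intention-to-treat.

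**The concern.** Two problems arise from the same procedure.

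First, whoever decides whether a patient has a language barrier, or asks the patient to take part, can already know the arm. Exclusions may then differ between arms for reasons related to the outcome. Removing controls who ask for information is the plainest case: it happens in one arm only and depends on interest in the subject, which is part of the main objective. An analysis of the patients who remain is not an analysis of all patients as randomised.

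Second, the visit schedule barely exceeds the target. If it is a ceiling, every ineligible patient beyond the sixth takes the trial below 330. If it is not, the protocol does not say how recruitment stays equal between doctors once the 8 days are over.

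**Working it through.** **Inputs, all from the Protocol.** Two-sided alpha 0.05 and power 80%: "Accepting an alpha risk of 0.05 and a beta risk of 0.2 in a bilateral contrast". Rates of completed directives 7.8% and 1%: "taking the rate of VAD in the intervention group as 7.8% and in the control group of 1"%. Method: "The POISSON approximation has been used in the statistical calculator GRANMO, version 7.12 online". Loss 10%; 7 doctors, 6 visits a day, 8 days.

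**Step 1: reproduce 165.** With Poisson variance,

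n = (1.960 + 0.842)² x (0.078 + 0.010) / (0.078 - 0.010)² = 7.849 x 0.088 / 0.004624 = 149.4 per arm.

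Dividing by 0.9 gives 149/0.9 = 165.6 (149.4/0.9 = 166.0), which agrees with 165 within rounding. So 165 already contains the 10%, and about 149-150 evaluable patients per arm (298-300 in all) carry the stated power.

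**Step 2: spare visits if 8 days is the limit.** 7 x 6 x 8 = 336; 336 - 330 = 6; 6/336 = 1.8%. For scale, the Introduction cites a survey in which 1.9% of Catalan respondents already had a directive. If that rate applied to these attenders, 336 x 0.019 = 6.4 visits would go on that one criterion, before language barrier, cognitive impairment or repeat visits.

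**Step 3: power if 8 days is the limit.** For an ineligible share s and refusal share r, n per arm = 168 x (1 - s) x (1 - r), and power = Φ(0.068 x √(n/0.088) - 1.960). Example with s = 10% and r = 10%: n = 136.1; 0.068 x √(136.1/0.088) = 2.674; Φ(0.714) = 76.2%.

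| Ineligible (assumed) | n per arm, 10% refusals | Power, Poisson | Power, pooled two-proportion | n per arm, no refusals | Power, Poisson |
|---|---|---|---|---|---|
| 0% | 151.2 | 80.5% | 82.5% | 168.0 | 84.4% |
| 1.8% | 148.5 | 79.8% | 81.8% | 165.0 | 83.8% |
| 5% | 143.6 | 78.4% | 80.6% | 159.6 | 82.5% |
| 10% | 136.1 | 76.2% | 78.4% | 151.2 | 80.5% |
| 15% | 128.5 | 73.8% | 76.0% | 142.8 | 78.2% |
| 20% | 121.0 | 71.3% | 73.5% | 134.4 | 75.7% |

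By the Poisson method, power falls below 80% above 1 - 149.4/151.2 = 1.2% ineligible with 10% refusals, and above 1 - 149.4/168 = 11.1% with none. By the pooled formula (142 per arm needed) the thresholds are 1 - 142/151.2 = 6.1% and 1 - 142/168 = 15.5%.

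**Step 4: days needed if recruitment continues.** At 7 x 6 = 42 visits a day and 10% refusals, days = 298 / (0.9 x (1 - s)) / 42. This gives 8.3 at 5% ineligible, 8.8 at 10%, 9.3 at 15% and 9.9 at 20%. Using 300 instead of 298 adds less than 0.1 day.

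**The case against.** A reader might infer that 336 visits is a hard ceiling and that the stated sample and power will therefore not be delivered. The documents do not support that. Recruitment procedure refers twice to completing the sample, once with a window of months, which is hard to square with a stop after 8 working days. The 6-visit, 8-day rule is presented as a way to balance doctors. A lost number does not cap enrolment either, because no list length is given. What stands against this reply is that the sentence joining the two limits by *or* can also mean whichever comes first, and that a completed sample is not defined as numbers used or as eligible patients enrolled.

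The shortfall near 2% is also slight. At 1.8% ineligible it is 0.2 points, and only if all 10% refusals occur; the Protocol itself says that, in principle, it expects no losses. This is correct, and a material loss needs roughly 10% ineligible or more.

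Because refusal is itself an exclusion criterion, the 10% does cover one kind of screening failure. That is fair, but nothing covers the other kinds.

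Finally, some exclusions (a coded diagnosis, an existing directive) can be read from the record and leave little room for judgement. That limits the first problem but does not remove it: language barrier and willingness to take part are judged or asked at the visit.

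**Conclusion.** The order of events needs correcting whichever recruitment limit applies. As written, eligibility and willingness are settled after the arm can be known, and those who fail are dropped, which does not fit intention-to-treat. Placing consent after the draw is an inference: it is sought through the physician, while the number is requested before the patient comes in. The documents do not allow the size of any resulting bias to be estimated, and they do not show that selective exclusion occurred.

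On numbers, the conclusion is conditional. If 8 days governs, expected power with 10% refusals is 79.8% at 1.8% ineligible and falls gradually to 71.3% at 20%; with no refusals it holds at 80% up to about 11%. If completion governs, the count is reached and the gap is the missing rule for equal recruitment after day 8. The figures assume equal arms and the plan's rates of 7.8% and 1% for completed directives. The documents give no ineligibility rate, so 0-20% is an assumed range. It would also be wrong to infer that the sample-size sum is in error: 165 per arm reproduces, and 336 does exceed 330.

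**What to change.** 1. Check eligibility and obtain signed consent before the number is requested. Ineligible and unwilling patients then use no number, and everyone randomised is analysed in the assigned arm, including controls who later ask for information.
2. State one stopping rule: all 7 doctors recruit for the same number of days, extended together until about 298-300 eligible, consenting patients (149-150 per arm) are randomised. A target of 330 at that stage would count refusal twice, since 330 already contains the 10%. This target assumes, as the Protocol does, no further losses; any allowance for follow-up loss should be added openly.
3. If the 8-day limit is kept, say so and restate the expected sample and power under a declared ineligibility rate.
4. Reconcile the 2015 and September 2016 recruitment windows.

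Cost: at 5-20% ineligible and 10% refusal, recruitment takes 8.3-9.9 days, so 9 or 10 whole days instead of 8. That is one or two more days per doctor, which fits even the one-month window, plus the change of wording.

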Parallel group unicentric randomized clinical trial. Prospective primary care intervention study.

For randomization, randomly generated numbers will be used in closed envelopes controlled by a professional outside the study. Subsequent masking is not appropriate for the patient. The randomization unit will be the patient.

Sample

Open-label (or non-blind) unicentric randomized clinical trial of parallel groups. Simple random sample of patients who go to an appointment with their family doctor.

Inclusion criteria: Patients older than 18 years old who go to their family doctor by appointment.

Exclusion criteria:

- Patients with language barrier
- Patients younger than 18 years (AD not provided for by law) (28)
- Patients with altered decision-making ability according to computerized clinical history by coding in health problems or mentioned in a clinical course of computerized medical history (eCAP): cognitive impairment, dementia, mental retardation diagnosed. Although there are studies on attitudes towards ADs of people with early cognitive impairment (Minimental > 18), it was decided to discard because the intervention should be brief. The cited study also concludes that this type of patients prefer to delegate decisions to the family. (29)
- Patients who come spontaneously to their family doctor.
- Patients who have already been recruited previously in the study. Patients who may visit by appointment only on more than one occasion will only participate once and subsequent visits for recruitment will be excluded. In addition, there will be no reinforcement of the study intervention in these visits.
- Patients who have already formalized the ADs.
- Patients who do not wish to participate in the study.

Calculation of sample size: In order to know the magnitude of the effect of similar studies in primary care with similar interventions (written and oral information vs no intervention), the Wissow study (25) was chosen, where the proportion of VAD obtained in intervention group was 7.8% vs. <1% in the placebo group.

In calculating proportions in cohort studies or clinical trials:

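### Control patients who want the information are excluded after allocation, in one arm only and with no time window, which conflicts with intention-to-treat and can favour the intervention

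*Protocol*

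**What the plan says.** **Allocation.** Under Recruitment procedure, the Protocol says of the random number: "This number will be asked prior to the patient's entry into the consultation".

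**Intervention arm.** Under Intervention, these patients "will be given brief information about the existence of the document of anticipated wills after resolving the reason for the visit", together with a leaflet. They receive it unasked. They show interest by acting afterwards: "In case of interest, you can leave your information in the User Service of the outpatient clinic", or by asking for a new appointment.

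**Control arm.** Controls are seen only for the reason they came. Then: "If the patient in this group wants the information, he will be excluded from the study", on the ground that the patient is refusing to participate. No period is stated. The next sentence says that a patient in either group who meets an exclusion criterion is recorded as a screening failure and the number is not re-used.

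**Refusals in general.** The exclusion criteria list "Patients who do not wish to participate in the study". Calculation of sample size gives this aim: "In order to avoid a selection bias produced by the relationship of giving up with the fact of wanting to do a VAD". The means it chooses to serve that aim is exclusion with a record of who left: "patients refusing to participate will be excluded and the motive, age and sex will be collected". These data are then set against each other by group.

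**Outcome and analysis.** The main objective is the proportion interested in or completing an advance directive within 3 months. Under Result or dependent variables, interest is the "Number of patients who have come to their family doctor (MF) to request information or have been interested by telephone in each group". The Limitations section plans contamination questions for controls who become interested or complete a directive. The Protocol's analysis section and the SAP both specify intention-to-treat; neither defines the analysis set.

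**The concern.** Randomisation protects the comparison only if patients stay in the arm to which they were allocated. Here patients leave after allocation, from one arm, for a reason tied to the outcome. No rule removes an intervention patient for wanting information; that patient is invited to ask for more.

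Wanting information is also not the same as declining to take part. The sample-size section itself names the link between giving up participation and wanting a directive as a selection bias, yet its remedy is to exclude. Collecting motive, age and sex shows who was removed but does not return them to the comparison.

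At stake is the interest-or-completion endpoint of the main objective. If the removed controls are those most likely to become events, the control rate is too low and the intervention looks better than it is.

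**Working it through.** **1. The plan's own figure.** The 165 per arm is for completion alone, 7.8% against 1%, two-sided 5%, power 80%. The Poisson formula gives n = (1.960 + 0.842)² × (0.078 + 0.010) / (0.078 − 0.010)² = 7.849 × 0.088 / 0.004624 = 149.4, so 150; 150 × 1.1 = 165. The figure reproduces. The problem is bias, not sample size.

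**2. Two readings of the missing window.**
- *Follow-up reading.* The rule applies for 3 months. It then also contradicts counting interest in each group and putting contamination questions to interested controls.
- *Index-visit reading.* The rule applies only at recruitment, as its place under Intervention suggests. Those two conflicts largely disappear. A request at that visit is then not clearly an outcome event, because intervention patients receive the same information unasked and count only if they act later.

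**3. Assumed inputs.** No true effect; the same event rate p in both arms; 149 per arm (165 × 0.9 = 148.5). The documents give no request rate, and the Protocol's hypothesis section says there is no earlier literature on interest. Results are exact probabilities for the uncorrected chi-square test at two-sided 5%. Removed controls leave both numerator and denominator.

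**4. Index-visit reading.** A share q of controls is removed, each k times as likely as average to become an event. The kept control rate is (p − q·k·p)/(1 − q). For q = 2%, k = 5, p = 10%: (0.10 − 0.01)/0.98 = 9.2%, against 10% in the intervention arm.

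| q, k | Two-sided error at p = 5 / 10 / 20% |
|---|---|
| 5%, k = 1 (no link) | 4.9 / 5.0 / 5.0% |
| 2% (3 of 149), k = 5 | 5.2 / 5.6 / 6.5% |
| 5% (7 of 149), k = 3 | 5.3 / 6.0 / 7.4% |
| 5%, k = 5 | 6.8 / 9.4 / 15.4% |

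In the second row, 3.5 / 4.2 / 5.5% favours the intervention, against about 2.5% without bias. At p = 20% and k = 5, k·p = 1: every removed control would have become an event, so 6.5% and 15.4% are the ceiling for those q.

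**5. Follow-up reading.** A share f of control events is removed. The analysed control rate is p(1 − f)/(1 − p·f). For p = 10%, f = 50%: 0.05/0.95 = 5.3%.

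| f | Two-sided error at p = 5 / 10 / 20% |
|---|---|
| 0 | 4.8 / 5.0 / 5.0% |
| 10% | 5.3 / 5.8 / 6.5% |
| 25% | 7.6 / 10.6 / 15.4% |
| 50% | 18.1 / 32.7 / 54.1% |

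At f = 50% nearly all of this favours the intervention (17.9 / 32.6 / 54.1%). At p = 1% the error stays near 3% for every f up to 50%. Fisher's test is lower: across p from 1% to 20% it gives 0.2 to 5.4% at f = 10%, and 0.2 to 50.7% at f = 50%. If every control event were removed, the control rate would be zero by construction; simulation with 165 per arm gives about 95% at p = 5% and about 100% at p = 10% and 20%.

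**6. Completion alone.** At the planned 1% control rate, removing every control who completes a directive moves the difference from 7.8 − 1.0 = 6.8 points to 7.8 points. That caps the effect at 1 point if the 1% is accepted. The documents do not show that such a bias would occur.

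**The case against.** The strongest reply is that the follow-up reading is unlikely. The sentence sits in the description of the index visit, and the plan collects reasons for completing, time to completion and characteristics of interested patients in both arms, which presupposes that interested controls stay in. On the index-visit reading, not wishing to participate is an exclusion criterion, and such patients could count as screening failures, which are recorded in both arms. The accurate charge would then be screening after allocation with an undefined intention-to-treat set, and the plausible bias is small.

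Much of this stands. The index-visit reading should carry more weight, the larger error rates belong mainly to the other reading, and no input has a source in the documents. It does not remove the point. Calling the patient a screening failure does not change that the trigger exists in one arm only and acts once allocation is known. Recording refusals and reporting to CONSORT makes the removals visible without undoing them. The text also does not say which reading is meant, so staff could apply either.

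It is also fair that the plan allows outcomes to be obtained by asking patients within 3 months, so the definition of interest must say whether interest voiced only when asked counts. That is a wording matter for both arms.

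**Conclusion.** The concern holds and should be fixed. Three things are certain from the text: the exclusion follows allocation, its trigger applies to controls only, and no window is given. It conflicts with the stated intention-to-treat principle on either reading.

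The direction depends on the reading. Over follow-up, each removed control event lowers the control rate and favours the intervention. At the index visit only, the direction is the same if removed controls would have become events more often than those kept; with no such link there is no bias.

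The size for the main endpoint is unknown. The calculated range runs from no inflation to a decisive one, and high error needs both common events and a large removed share. Every rate behind that range is an assumption, and the documents do not settle which reading is intended.

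**What to change.** - Delete the exclusion. Keep every randomised, eligible, consenting control in the assigned arm and in a defined intention-to-treat set, followed to 3 months for completion by contact or through eCAP.
- Define interest identically in both arms: a request by visit, User Service or telephone, after the index visit and within 3 months. State whether interest voiced only when asked at follow-up counts.
- Record a control's request at the index visit, and any information given, as a crossover and not as interest in the main analysis. Scoring it in controls alone would reverse the bias: with q = 2%, the control rate becomes p + q(1 − p), and false positives against the intervention are 9.7 / 7.1 / 5.3% at p = 5 / 10 / 20%, instead of about 2.5%. Add a sensitivity analysis that counts these requests, reported as a bound.
- Reserve the refusal label for patients who decline or withdraw consent. State that the contamination questions do not lead to exclusion. Report all exclusions after allocation by arm, with reason.

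**Cost.** Wording changes in the Protocol (Calculation of sample size, Intervention, Result or dependent variables, Limitations) and two definitions in the SAP. The sample size is unchanged. Controls who receive information will dilute the contrast slightly. Those who decline or withdraw consent still cannot be followed.

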A systematic review of 2008 that evaluated the effectiveness of different interventions to promote early will in the elderly showed that most studies conducted a single educational session and measured outcomes over the next 6 months. The mean OR calculated for the performance of the document in the intervention groups was 2.6 (15). In another similar systematic review but whose population was non-terminal patients, it was observed that the majority of studies were of low quality and in the most rigorous the OR was 2.42 for different educational interventions (written materials, videos or audios).

Different ways of increasing the realization of DVA have been studied: written material only, written material with a single educational session or written material, and educational sessions. In a review of the the literature of 2007 concluded that only the multifaceted modalities increased the interest of the patients to talk about the subject with their doctors.

Tamayo et al. also observed in another systematic review that the best intervention to increase the proportions of DVA is the combination of informational material and repeated conversations in clinical visits (18).

Studies carried out in Primary Care

It is striking the good acceptance by the population towards the DVA and the scarce record of it. Angora et al., In a study in which patients aged over 65 years were interviewed in a primary care center, found that the patients were in agreement with the possibility of performing the document despite the underutilization of this resource (19). Santos et al., Also through primary care surveys, found that 97% considered it interesting, 39% said they would, and 86% did not feel uncomfortable talking to their family doctor (20). Similar results were obtained by Llordés et al. in corroborating that there was little information and much interest in this process (21).

The citizens' assessment of the possibility of making a document of advance directives is very positive, but only 1.9% in Catalonia and 0.5% in Andalusia of the respondents had done it (22,23). In Andalusia, it was also seen the importance of the information leaflet in the health center to increase satisfaction. (23)

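### The interest outcome may be obtained by asking the patient, and no rule keeps a yes to the study's own question from counting as an event

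*Protocol*

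**What the plan says.** The main objective in the protocol, repeated in the SAP, is the proportion of patients interested in an AD or completing one within 3 months. The SAP analyses this as a yes/no variable, by a two-sample comparison of proportions and by logistic regression.

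The protocol section Result or dependent variables gives one collection rule for the outcomes. They are recorded when the patient shows interest or, failing that, "by asking by appointment or by telephone within 3 months of their recruitment". The interest item is then defined as: "Number of patients who have come to their family doctor (MF) to request information or have been interested by telephone in each group". The first half describes something the patient does. The second half does not say who placed the call.

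Two other places bear on the point:

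- Under Intervention, the intervention arm is told of a further way to respond: "In case of interest, you can leave your information in the User Service of the outpatient clinic".
- Also under Intervention, a control who wants the information is excluded as a refusal. No time limit is attached to that sentence.

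The SAP does not separate spontaneous from prompted interest.

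**The concern.** Asking is the fallback for every patient who has not come forward, which is likely to be most controls. The intervention is itself a short mention of the document plus a leaflet. Asking a control whether he is interested tells him that the document exists, which is part of what the control arm is meant not to receive. If his yes is then scored, the measurement has produced the event.

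The protocol's own background suggests that a yes is not hard to obtain. One cited primary care survey "found that 97% considered it interesting, 39% said they would, and 86% did not feel uncomfortable talking to their family doctor". Those questions are not the one this study would ask, so the figures show plausibility only.

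At stake is what the main comparison means. A composite that mixes requests made by patients with agreement to a study question does not estimate the effect of the intervention on seeking an AD. If date and initiator are not recorded, the two cannot be separated afterwards.

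**Working it through.** **Inputs from the protocol (Calculation of sample size).** Design: "Accepting an alpha risk of 0.05 and a beta risk of 0.2 in a bilateral contrast". AD completion is taken as 7.8% vs 1%. Loss: "A rate of loss has been estimated for refusing the 10% share". Result: "165 individuals in the intervention group and 165 in the control group are required". The method is a Poisson approximation.

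**Reproducing the plan's figure.** With the variance set equal to the rate,

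n = (z₀.₉₇₅ + z₀.₈₀)² × (p₁ + p₀) / (p₁ − p₀)² = 7.849 × 0.088 / 0.068² = 149.4 per arm.

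Allowing for 10% loss gives 149.4 × 1.1 = 164.3, rounded up to 165 (or 149.4 / 0.9 = 166). The stated 165 reproduces. It is sized on completion alone; the protocol's Hypothesis section says there is no earlier literature on interest.

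**Assumptions (not in the documents).** Let u be the unprompted event rate in an arm, and q the share of the remaining patients who say yes when asked. The counted rate is p = q + (1 − q)u. With equal q in both arms, the difference becomes (1 − q)(u₁ − u₀) and the ratio moves towards 1. Power is by exact enumeration of two binomials, 165 per arm, uncorrected chi-square test, two-sided 5%.

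Case 1: unprompted rates equal to the planned completion rates, 7.8% vs 1%.

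| q | Intervention | Control | Difference (points) | Ratio | Power |
|---|---|---|---|---|---|
| 0 | 7.8% | 1.0% | 6.8 | 7.8 | 91% |
| 1% | 8.7% | 2.0% | 6.7 | 4.4 | 81% |
| 5% | 12.4% | 6.0% | 6.5 | 2.1 | 54% |
| 10% | 17.0% | 10.9% | 6.1 | 1.6 | 36% |
| 39% | 43.8% | 39.6% | 4.1 | 1.1 | 12% |

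Example, q = 5%: 0.05 + 0.95 × 0.078 = 0.124 and 0.05 + 0.95 × 0.01 = 0.060. A normal-approximation formula gives 86% at q = 0 and 53% at q = 5%; the pattern is the same.

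Case 2: a larger assumed effect on interest, 20% vs 1%.

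| q | Intervention | Control | Difference (points) | Ratio | Power |
|---|---|---|---|---|---|
| 0 | 20.0% | 1.0% | 19.0 | 20 | >99% |
| 10% | 28.0% | 10.9% | 17.1 | 2.6 | 98% |
| 39% | 51.2% | 39.6% | 11.6 | 1.3 | 57% |

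**Unequal prompting.** Take the 7.8% vs 1% rates.

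- q = 10% in the intervention arm and 5% in control gives 17.0% vs 6.0%, a difference of 11.1 points, larger than the true 6.8.
- The reverse gives 12.4% vs 10.9%, a difference of 1.5 points.
- With no true effect (1% in both arms), 10% vs 5% prompting gives 10.9% vs 6.0%. The test then rejects in about 37% of trials.

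So the direction is not fixed.

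**The case against.** The strongest reply is that the definition describes past behaviour. It counts patients who came to request information, and the awkward telephone phrase may be a rough translation of having enquired by telephone. The same asking rule covers completion, where it can only mean asking whether the document was made; the parallel question for interest is whether the patient asked for information. The contamination questions under Limitations and ethical considerations fit this, because they look outside the study's call for the source of a control's interest. No call script asks patients whether they are interested. This stands as a plausible reading. A reader might infer that the protocol orders prompted answers to be counted, and it does not. But nothing in either document excludes them.

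A reader might also infer that prompting must drown the arm difference. That is not supported either:

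- Case 1 uses completion rates for an outcome that should be commoner than completion, and Case 2 keeps good power at q = 10%.
- The survey answers do not measure q.
- The trial is open-label, and the protocol itself warns of a raised response in the intervention arm through the link with the family doctor.
- The sentence excluding a control who wants the information, if applied during follow-up, would remove control events and so push the other way.

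Finally, a reader might infer that User Service requests are lost when a patient cannot be reached at 3 months. The text does not say so. Outcomes are recorded when interest is shown, without restriction of route, and the record lookup is a fallback that erases nothing already noted. The interest definition simply does not name that route.

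**Conclusion.** The point holds as an ambiguity with consequences: a yes to the study's own question can count as an event in the main composite, and neither document prevents it. With equal prompting in both arms, the difference and the ratio shrink for any q above zero. The loss of power ranges from severe (91% to 54% at q = 5%, with unprompted rates of 7.8% vs 1%) to small (still 98% at q = 10%, with 20% vs 1%). Both the unprompted interest rates and q are assumptions. With unequal prompting the bias can go either way.

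This should be fixed but does not invalidate the trial. AD completion is recorded as its own yes/no variable, is the basis of the sample size, and is not redefined by this problem.

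**What to change.** In Result or dependent variables and in the SAP:

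1. Define interest as a request for AD information that the patient initiates after the recruitment visit and before the 3-month study contact, by any route (family doctor, the patient's own call, User Service). Record date, route and initiator in the same way in both arms.
2. At 3 months, use one fixed script in both arms that asks only about past behaviour: whether the patient has asked anyone for AD information since the recruitment visit, and whether an AD has been made.
3. Report interest first expressed in reply to the study's question separately, as descriptive data, and do not count it as an event.
4. Reconcile this with the sentence under Intervention that excludes a control who wants the information. State whether a control's later request is an event or an exclusion.

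The cost is a revised definition, a short script, a few extra fields and reading the User Service requests. Sample size, visits and intervention stay as they are. The downside is fewer interest events and some reliance on recall for requests that left no record.
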